The technology relating specifically to Virtual Reality has seen significant changes in the last 5 years. Previously, Virtual Reality devices required either a direct connection to a local computer or even a dedicated system to run them. New to the market in the last few years are devices which do not require a connection to a computer, phone, or internet for some functions. This is significant as these devices can be used in any environment with minimal equipment. Additionally, Malloy and Milling report that the use of more sophisticated technology with improved immersion is associated with even greater relief of pain. Although there are alternative methods for anxiety and pain control in the emergency setting, the use of immersive virtual reality (virtual reality methods in which the user is able to interact with the virtual environment) with these new standalone devices may improve pain control and anxiety associated with procedures, decreasing the need to use anxiolytics, opioids, and anesthetics in the emergency department. If a significant difference is found between the standard practice of performing venipuncture without pain control or virtual reality and the standard practice with the addition of virtual reality, then there would be strong implications to utilize the method in the emergency department setting. This could lead to future studies on additional procedures

with VR such as laceration repair, nail trephination, digital blocks, nail removal, lumbar punctures, and incision and drainage of abscesses.

In order to support the hypothesis of this study, which is that there will be a clinically significant decrease in pain perception when patients use virtual reality devices during venipuncture, a literature review was conducted focusing on articles published from 2000 to present using key terms *virtual reality*, *pain control*, *distraction*, and *procedure related anxiety*. The review was conducted on databases such as Pubmed, Ovid, Cochrane, Medline, Google Scholar, and a hand search through references used in applicable articles. A total of 60 articles were reviewed for relevance. Of the 60 reviewed articles, 23 were selected for their relevance to the research question. The literature review shows no studies of note have been conducted which would be applicable to an adult population for similar procedures (ie. venipuncture).

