Once approved for participation in the study all participants will undergo a brief instructional class on how to operate the HMD and will be allowed sufficient time to become comfortable with its use. We expect approximately 5-10 minutes to be required for this portion of the study. Once familiar with the use of the VR headset, participants will be asked to randomly draw an envelope from a container. This envelope will contain a block and sequence number. The block and sequence number will be the subject ID and will correspond to a predetermined number set on a separate document that will determine if the participant will use the HMD during venipuncture or not. The screener will not have immediate access to the list showing which group the participant will be assigned to. One member of the study team will be present in the lab room to ensure the participant uses the VR headset (or not) according to what is randomly drawn. This member of the research team will have the list showing whether or not the participant is assigned to the control arm or the experimental arm. The participants will then proceed to the specimen room to undergo venipuncture.

Venipuncture for both groups will occur in the non-dominant arm. The reasoning for this is that the Oculus Go requires one free hand to use a controller. This will ensure that the individuals participating are able to effectively use the device. Those unable to undergo venipuncture in the non-

dominant arm will undergo venipuncture in the dominant arm instead and will use the Oculus Go controller with their non-dominant hand.

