Those utilizing the Oculus Go HMD will be interacting with the VR game Ocean Rift. They will utilize a single controller to explore an underwater safari park. Ocean Rift has multiple environments to choose from, including coral reefs, ship wrecks, lagoons, the arctic, and prehistoric seas. Participants may interact with and learn about different creatures to include dolphins, turtles, orcas, ray, whales, sea lions, manatees, and dinosaurs. During the game users may travel where they please and interact with what they choose. The VR device is equipped with head-tracking software that allows the user to choose direction by looking around. The entire interior and exterior of the headset will be cleaned with alcohol-based wipes after each use. Alcohol will be used since it is generally well-tolerated on human skin, and since it evaporates quickly. The headset will be dried in the open air for a minimum of two minutes between each subject's use.

Those not using the VR will still wear a headset that will simply be turned off. This is to ensure that any significant change noted with the VR is due to the use of VR itself, and not simply due to "blindfolding" the patient during the procedure.

As some patients experiencing anxiety may be tempted to move during the procedure, lab personnel will instruct participants to remain still during venipuncture. Participants will be advised that they may take breaks as needed if anxiety becomes overwhelming.

After undergoing the procedure, each participant will be asked to fill out the post-procedure questionnaire and return it to the study team member present in the lab room, who will clean the headset as the participant completes the questionnaire. This questionnaire assesses the patient's pain intensity and level of anxiety with the VAS similar to the VAS shown above, as well as the patient's satisfaction with the visit which will be measured utilizing a Likert scale for individual questions (see below).

Overall, how satisfied were you with the use of Virtual Reality in reducing your pain level?

5 Very Satisfied	4 Satisfied	3 Not Sure	2 Unsatisfied	1 Very Unsatisfied
---------------------	----------------	---------------	------------------	-----------------------

Overall, how satisfied were you with the use of Virtual Reality in reducing your anxiety level?

5 Very Satisfied	4 Satisfied	3 Not Sure	2 Unsatisfied	1 Very Unsatisfied

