11.5 Please provide a justification for your sample size

A study performed by Todd et al 1995 and a later validation study by Gallagher et al 2001 both found that a minimum clinically significant change in pain as measured on the VAS is 13mm. Both studies found that the change in pain reported as "a little more pain" or "a little less pain" after intervention averaged to 13mm. Both studies also found that the standard deviation of change in pain reported on the VAS as "a little more pain" or "a little less pain" was 17mm.

Since the t-test will be used at the end of the study to determine if the effects are statistically significant, the E/S ratio (expected effect size divided by the standard deviation of the outcome variable) was used to determine the sample size. The E/S ratio is being estimated based on the studies cited above. The expected effect size (13mm) divided by the standard deviation (17mm) =0.76. To ensure a 2-sided α 0.05 and β 0.20, a minimum of 27 subjects are required for each arm. This is based on a sample size calculator created by Dhand et al as well as appendix 6A of *Designing Clinical Research* authored by Hulley et al.

Although a total of only 54 participants is required for this study to be effectively powered, we're requesting 60 to account for a potential dropout rate of 10%.

Minitab software will be utilized for final data analysis.

11.6 Data Analysis Plan: Complete description: Background, Objectives, Design, Step by Step how the project is going to be done, Data analysis plan:

The primary outcome be measured as the average pain rating between the two groups as measured on the VAS. The t-test will be used to compare the two groups to determine if the difference is statistically significant. The difference between the two groups should be at least 13mm to be considered clinically significant.

The preprocedural anxiety will also be measured using the VAS and the average difference will be reported in the data, although a minimum clinically significant score is not available.

Since participants will be randomly assigned to each study arm, it will be impossible to insure an even spread of ages between the two study arms. It may be possible that pain perception changes with age, and since this study will include ages 18-50, data tables comparing the average changes between those in different age groups (i.e. 18-25, 26-33, 34-41, 42-50). A separate subgroup analysis will be performed comparing different age subgroups.

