13.0 Recruitment and Consent

13.1 Please describe the recruitment process, including how subjects will be identified and selected for the study.

When approaching the ticket stand to draw a waiting number for the lab, prospective participants will be asked by an assistant investigator located near the kiosk if they are interested in participating in the study. Participants will be selected in consecutive order (as long as the screening room is open) to avoid selection bias. However, patients who are obviously outside of the age range of 18-50 will not be asked to participate, although this process may leave room for some selection bias. If participants express desire, they will move to a screening station located in a private room near the lab to be educated on the details of the study, to include any risks. If they consent, they will fill out a screening questionnaire. If patients are eligible, they'll be given a brief tutorial on use of the VR headset and randomly assigned an envelope containing a card stating that they will use VR during venipuncture or undergo standard practice (the researcher will be blind to which group the participant is assigned to). Once instruction is complete, they'll return to the lab waiting area to draw a ticket to provide a specimen IAW standard lab practice.

13.2 Compensation for Participation:

There will not be any compensation (payment or otherwise) for participating in this study.

13.3 Please describe the pre-screening process. If no pre-screening, enter Not Applicable in the text editor

When patients approach the ticket kiosk, a member of the study team will ask them if they're interested in participating in a study related to pain control with venipuncture. To avoid perceived coercion, the recruiter will be in scrubs so that his rank will not be visible. If the participants wish to participate, they'll be directed to a screening station in a private room.

At the screening station, candidates will be screened to insure they meet inclusion/exclusion criteria by completing a prescreening form that addresses all participation criteria. After that, they'll be provided informed consent documents and will undergo a brief tutorial for use of the VR headset prior to returning to the lab waiting area to draw a ticket.

13.4 Consent Process:

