- If you begin to experience nausea, headache, eye strain, or any other discomfort, please remove the headset and inform a member of the research team immediately

Participants will also be advised to request breaks as needed if they experience uncontrollable anxiety, or they may withdraw if they request as stated in the consent form.

To minimize the risk of patients moving arms during venipuncture, phlebotomists will be asked to alert the patient that they are about to penetrate the skin and to hold still.

To minimize the risk of loss of confidentiality, all information collected will be controlled with strict record keeping procedures. All de-identified data collected will be stored in a locked drawer behind a locked door when not in use and only accessible to the research team members. Once gathered, the data will be transferred into electronic form on a secure CAC-enabled/password protected government computer that will be in the possession of the PI, when not in the PI's possession it will be stored in a locked room. The electronic documents will be kept for 3 years and then deleted. There will be no legal or economic risks associated with this study. No adverse action will be taken against anyone who withdrawals from the study at any time.

14.3

Confidentiality Protections (for research records, data and/or specimens):

Describe in detail the plan to maintain confidentiality of the research data, specimens, and records throughout the study and at its conclusion (e.g., destruction, long term storage, or banking). Explain the plan for securing the data (e.g., use of passwords, encryption, secure servers, firewalls, and other appropriate methods). If data will be shared electronically with other team members/collaborators outside the institution, describe the method of transmission and safeguards to maintain confidentiality. Explain whether this study may collect information that State or Federal law requires to be reported to other officials or ethically requires action, e.g., child or spouse abuse

All de-identified data collected will be stored in a locked drawer behind a locked door when not in use and only accessible to the research team members. Once gathered, the data will be transferred into electronic form on a secure CAC-enabled/password protected government computer that will be in the

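### Nothing masks the phlebotomist or keeps needle technique and wording the same by arm, so performance bias in the pain score is possible; partial masking and one fixed wording would be a cheap improvement

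*Combined protocol and SAP*

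**What the plan says.** The primary outcome is pain on a 100 mm visual analogue scale, marked by the participant immediately after the draw (11.1). The arms are compared by a t-test, and a difference of at least 13 mm counts as clinically significant (11.1, 11.6).

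Two spoken instructions surround the needle. In 10.1, "lab personnel will instruct participants to remain still during venipuncture". In 14.2, "phlebotomists will be asked to alert the patient that they are about to penetrate the skin and to hold still". Neither is limited to one arm, and neither has fixed words or timing.

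Concealment is described for one role only. Section 10.1 says the screener has no immediate access to the allocation list, and 13.1 says "the researcher will be blind to which group the participant is assigned to". In the lab room, 10.1 places a study team member who holds the list and sees that the assigned arm is followed.

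On equipment, 10.1 says: "Those not using the VR will still wear a headset that will simply be turned off". The stated reason is to separate the effect of VR from that of being blindfolded; masking of staff is not mentioned. VR participants steer with a hand controller and by looking around. No controller is described for control participants during the draw.

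**The concern.** The phlebotomist produces the stimulus whose pain is the primary outcome, and speaks to the participant just before it. A phlebotomist who knows the arm may, without intending to, insert the needle more gently, reassure more, steady the arm more or warn more firmly in one arm.

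Any such difference enters the mean pain difference. The planned t-test is unadjusted, and the variables in 10.2 include nothing on the operator, the number of attempts or what was said. The analysis could therefore not separate it from VR.

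The direction is open. Extra care for one arm could create a difference, and extra care for the other could hide one. Participants cannot be blinded to whether the headset is running, so the operator is one of the few sources of bias that the design can still limit.

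**Working it through.** **1. Who is kept from the allocation.**

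| Role | What the plan says | Can learn the arm? |
|---|---|---|
| Screener / researcher | No immediate access to the list (10.1); blind at assignment (13.1) | Kept from it at assignment |
| Team member in lab room | Holds the list, enforces the arm (10.1) | Yes, by role |
| Phlebotomist | Nothing | Yes: works beside the list holder; VR users move the head and use a controller |

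That the phlebotomist is unmasked is a reading of silence. But the plan names who is blind, leaves this person out, and describes visible signs of the arm.

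**2. Whether the two instructions conflict.** They do not. A general instruction to stay still and a warning just before insertion can both be given, and both apply to all participants. What is missing is anything that keeps their delivery the same in the two arms.

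**3. The plan's own sample size.** Section 11.5: "The expected effect size (13mm) divided by the standard deviation (17mm) =0.76" and "To ensure a 2-sided α 0.05 and β 0.20, a minimum of 27 subjects are required for each arm". By the normal approximation, n per arm = 2 × [17 × (1.960 + 0.842) / 13]² = 26.8, so 27, as stated. Adding 10% dropout gives 54 / 0.90 = 60, also as stated. Neither figure is in dispute.

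**4. What an arm shift would do (illustration).** Inputs from 11.4 and 11.5: SD 17 mm, two-sided alpha 0.05, 27 per arm (minimum) or 30 per arm (enrolled). The shifts of 2, 3 and 5 mm are assumptions; the documents give none.

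- Standard error of the difference = 17 × √(2/n): 4.63 mm at 27 per arm, 4.39 mm at 30.
- Smallest difference that is significant = t critical value × SE: 2.007 × 4.63 = 9.3 mm at 27; 2.002 × 4.39 = 8.8 mm at 30.
- With no VR effect and a shift b, the rejection rate comes from the noncentral t distribution with noncentrality b / SE. For b = 5 at 27 per arm this is 5 / 4.63 = 1.08.
- The chance of an observed difference of at least 13 mm in the favoured direction is 1 − Φ((13 − b) / SE). For b = 5 at 27 per arm: (13 − 5) / 4.63 = 1.73, which gives 4.2%.

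| Assumed shift | t-test rejects, 27 / 30 per arm | Difference ≥ 13 mm, 27 / 30 per arm |
|---|---|---|
| 0 mm | 5.0% / 5.0% | 0.2% / 0.2% |
| 2 mm | 7.1% / 7.3% | 0.9% / 0.6% |
| 3 mm | 9.8% / 10.3% | 1.5% / 1.1% |
| 5 mm | 18.6% / 20.2% | 4.2% / 3.4% |

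The two result columns answer different questions. The first applies if the report claims statistical significance alone. The second applies if it also holds to the plan's 13 mm threshold, which is the stricter bar.

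**The case against.** The strongest reply is that the planned procedure is the same in both arms. The alert goes to every patient, everyone wears a headset, and the same rule decides which arm of the body is used. Section 14.1 calls accidental movement unlikely because the phlebotomist steadies the limb. Section 10.1 links movement to anxiety and not to VR, so the prompt might even be needed less in the VR arm. All of this stands. Unequal delivery is a possibility that the plan leaves open, not something it plans.

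A reader might infer more: that the warning breaks the VR distraction and costs power, since 9.2 says "the use of more sophisticated technology with improved immersion is associated with even greater relief of pain". The documents do not support this. That sentence is about technology and not spoken cues. A warning given equally to all belongs to the comparison of standard practice with and without VR, so any dilution it causes is part of the effect being estimated and is not bias. Nothing in the documents allows such a loss to be quantified.

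It is also fair to say that masking can succeed only in part, and that participants know their arm and rate their own pain. The fix leaves that expectation effect untouched. These limits reduce the gain, but they do not remove the case for a change that uses staff and equipment already in the room.

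**Conclusion.** The point holds as a cheap improvement to the design. The plan leaves the person who delivers the stimulus unmasked, and it does not keep technique or wording the same by arm, so performance bias in either direction is possible.

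Its size cannot be derived from the documents. Under the assumed shifts of 2 to 5 mm, with SD 17 mm and 27 to 30 per arm, the t-test false-positive rate would be about 7-20% instead of 5%. The chance of reaching 13 mm by bias alone would be about 1-4%. A conclusion that rests on both criteria is therefore much better protected than one that rests on the p-value.

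Sections 10.1 and 14.2 should not be read as contradicting each other, nor the alert as directed at VR users. The sample size is unaffected.

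**What to change.** Amend 10.1 and 14.2 as follows.

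1. The team member already in the lab room sets the headset on or off and does not state the arm to the phlebotomist. Where lab flow allows, this is done before the phlebotomist begins.
2. Control participants hold the controller in the same hand as VR participants would.
3. The instructions in 10.1 and 14.2 are given in one fixed wording at the same point of the draw in both arms. The study team and the lab settle the content, so that its safety purpose is kept.
4. The report states that the operator was at most partly masked. Recording the phlebotomist's guess of the arm after each draw is optional and would show how far masking worked.

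The cost is protocol wording and a short briefing, with no change to the 60 participants. The main limit is that VR users look around and use the controller, so some phlebotomists will still recognise the arm. The fixed wording helps even then. Data collection is expected to last only 3-4 days (16.1), so this should be settled before the first participant.

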15.0 Study Monitoring

15.1 Your study requires either Data and Safety Monitoring Plan (DSMP) or a Data and Safety Monitoring Board (DSMB).

- DSMP
- DSMB
- Both
- Not Applicable

16.0 Reportable Events

16.1 Reportable Events: Consult with the research office at your institution to ensure requirements are met. Describe plans for reporting unexpected adverse events and unanticipated problems. Address how unexpected adverse events will be identified, who will report, how often adverse events and unanticipated problems will be reviewed to determine if any changes to the protocol or consent form are needed and the scale that will be used to grade the severity of the adverse event.

Consult with the research office at your institution to ensure requirements are met

- Describe plans for reporting expected adverse events. Identify what the expected adverse events will be for this study, describe the likelihood (frequency, severity, reversibility, short-term management and any long-term implications of each expected event)
- Describe plans for reporting unexpected adverse events and unanticipated problems. Address how unexpected adverse events will be identified, who will report, how often adverse events and unanticipated problems will be reviewed to determine if any changes to the research protocol or consent form are needed and the scale that will be used to grade the severity of the adverse event

Expected possible adverse events for this study are as follows:

Headache
Dizziness
Eye strain
Blurred vision
Muscle twitching
Eye strain
Disorientation
Excessive sweating
Loss of balance

The incidence of these events are not well-defined, so it's difficult to estimate the likelihood of these events occurring. However, participants will be instructed to discontinue the use of the headset if any of these symptoms, or any other discomfort occurs. If participants experience any of these symptoms and discontinue the use of the device, they will be monitored briefly by the research investigators as these symptoms should resolve spontaneously and should not have long-term implications. If symptoms do not resolve within 10-15 minutes, they will be escorted to the emergency room for further evaluation.

Expected adverse events will be reported by the principal investigator in the same fashion as unanticipated problems (stated below). As data collection is only expected to occur for 3-4 days, investigational staff will be reviewed after each adverse event to determine if changes need to be made to the research protocol or consent form.

The only known unanticipated problem involving risk to subject or others (UPIRSO) is seizure. As stated in the Oculus Go user manual, this has an incidence of approximately 1 in 4,000 users, although it most commonly occurs in children (who are excluded from the study). In the event that this occurs, subjects will have all sharp objects moved away from them, be placed laterally on their sides, and emergency personnel will be contacted for transport to the ER for further evaluation and treatment.

Unanticipated problems involving risk to subjects or others will be reported promptly providing initial notification of the event as quickly as possible after the research team's knowledge of the event, but within (5) business days of identification by [contact]), by e-mail ([contact]), or by [contact]) to the Office of the Regional Health Command Central (RHC-C) Institutional Review Board (IRB). A complete written report will follow the initial notification within ten (10) business days. The complete report will be sent to the RHC-C IRB Office I, Brooke Army Medical Center, ATTN: MCHE-ZQ, Department of Quality and Safety, [name].

To fulfill the local responsibility for monitoring and oversight of research, all potential UADEs that are unexpected and determined to be at least possibly related or definitely related to research participation

will be promptly reported within 24 hours of learning of the event by telephone or by email to the local IRB Office. A complete report will follow the initial notification within 5 business days.

